Study Design. This double-blind, randomized pilot clinical trial will prescreen an estimated 250 potential subjects, consent and further evaluate approximately 100 potential subjects, and ultimately enroll 70 subjects to ensure 40 subjects will provide a primary marijuana reduction outcome measure at four weeks post quit date. Subjects will be stratified by sex then randomized to one of two treatment groups (n=20 per drug group, 50% female): progesterone (PRO; 200mg 2x/day) or Placebo (PBO). They will take the medication for 5 weeks and will attend weekly clinic visits (see Visit Sequence & Procedure below for more information).

Setting: This project will be conducted at the Delaware Clinical Research Unit (DCRU). The DCRU has both inpatient and outpatient resources for the spectrum of biomedical research including special capabilities that were developed for study of substance use disorders. The Clinical and Translational Sciences Institute (CTSI), runs the DCRU and functions parallel to and supports the activities of the NIH funded CTSI, which it predicated. The DCRU includes: reception area, examination rooms, meeting rooms, clinical interview rooms, testing rooms for computer based performance tasks, a wet lab for handling bloods and other specimens, freezers (to -80°C), all essential staff offices, each with multiple telephone and computer lines through the University of Minnesota servers, locked limited access protocol, equipment and medication rooms, as well as secure cabinets for study files and essential supply and support areas and services.

Recruitment: To meet recruitment goals, we aim to enroll a total of 70 subjects (~6 subjects/month) to ensure a final sample size of 20 females and 20 males completing the study. Our primary recruitment method will be advertising in the mainstream media. While this type of recruitment can be challenging, our team has been successful with this form of recruitment. For example, our current study (PRO for smoking cessation) has had success with Facebook, Craigslist, TV, and radio advertising. Specifically, over the past seven months, we have received an estimated 300 phone calls from interested participants which resulted in the enrollment of 30 subjects (~8 subjects/month).

Study Sample. This study will enroll males (n=35) and females (n=35) who self-report use marijuana ≥4 days per week and are interested in changing their marijuana use. Specific eligibility criteria are as follows:

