Baseline Visit (Visit 3): Female subjects will be instructed to come into the clinic within three days of the start of their Luteal Phase for their baseline visit and to start medication (PRO or PBO). Female subjects will self-report menstrual cycle length at their screening visit and staff will determine when their Luteal Phase will most likely begin. Male subjects will be instructed to come into the clinic according to their assigned delay (per randomization list generated by the Statistical Analysis Core). This visit will occur seven days prior to quit date. At this visit, subjects will be randomized to PRO or PBO within strata defined by sex. The Statistical Analysis Core (SAC) will generate the randomization tables (one for each sex, 1:1 allocation using randomly permuted blocks of size 2 and 4), and the Clinical Trials Research Pharmacy will use it to determine randomization assignment. Randomization assignment will be stored in a secure file in a secure location at the Clinical Trials Research Pharmacy, to be shared only with the SAC. All other project staff including PI and study coordinator, as well as the participant, will remain blinded to the randomization assignment. At the baseline visit subjects will provide a blood sample (for hormone assessment), urine sample for THC, breath sample (to confirm smoking status via carbon monoxide breathalyzer), have their vital signs (blood pressure, heart rate, weight) measured, be informed of their quit date, and receive brief behavioral counseling to prepare for their quit date. At the end of this visit subjects will be compensated for their time, given study medication along with instructions for taking the medication (beginning at 8PM that day), as well as a clinic visit schedule for the remaining clinic visits. This visit will take approximately one hour to complete.

Marijuana Change Date Assignment: Change date (Week 0) will be set for 7 days following the Baseline Visit. Since this entails a delay of variable duration from Screening Visit 2 to Baseline Visit (thus impacting timing of medication initiation) across female subjects, each male subject will be matched to a female subject for a similar delay so that, across the male and female groups, study procedures will follow a similar chronology.

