Addressing Hypothesis 1a: An unadjusted assessment of the treatment effect will come from a linear model of percent reduction in marijuana use on randomized treatment assignment, separately by sex. **Hypothesis 1b:** A linear model including both males and females will be used to estimate the overall gender effect on percent reduction in marijuana use. **Hypothesis 1c:** A linear model including both males and females will be used to estimate the association of serum progesterone with percent reduction in marijuana use; we will separately consider baseline progesterone, cumulative progesterone (summed over weeks 0-4), and week 4 progesterone.

Addressing Hypothesis 2a: A linear model including both males and females will be used to estimate the association of impulsivity with percent reduction in marijuana use. **Hypothesis 2b:** A linear model including both males and females will be used to estimate the interaction between baseline impulsivity and baseline serum progesterone on percent reduction in marijuana use.

Missing data plan: Quality assurance plans are described below. The primary outcome analysis will be carried out using two parallel models: one model will exclude subjects for whom we were unable to obtain a week 4 TLFB or urine THC. Since 'missing at random' is a strong statistical assumption to make, we will also carry out a parallel model that uses multiple imputation of the week 4 TLFB and urine THC based on an individual's previous visits' TLFB and urine THC levels. We will also examine whether persons missing their week 4 visit differed in their baseline characteristics or treatment assignment from persons not missing their week 4 visit.

Power: This is a pilot study to generate data to potentially motivate and justify a future fully-powered study of PRO and marijuana use. This study will estimate magnitude and direction of treatment effects and associations with impulsivity (sex-specific and overall). Hence, no power calculations are provided.

Data Safety and Monitoring Plan, Board, and Administration.

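### Multiple imputation is offered because missing at random is doubted, yet it rests on that assumption, and the text available has no sensitivity analysis for loss that is not at random

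*Combined protocol and SAP*

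**What the plan says.** The Analysis Plan defines the primary outcome as Week 4 TLFB marijuana use relative to baseline. It includes in the main analysis everyone randomized who has that outcome measured. Its missing data plan then sets out two parallel models:

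- **Complete-case:** "one model will exclude subjects for whom we were unable to obtain a week 4 TLFB or urine THC".
- **Imputed:** introduced with "Since 'missing at random' is a strong statistical assumption to make, we will also carry out a parallel model that uses multiple imputation", and specified as "imputation of the week 4 TLFB and urine THC based on an individual's previous visits' TLFB and urine THC levels".

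The same paragraph promises to examine whether persons missing Week 4 "differed in their baseline characteristics or treatment assignment from persons not missing their week 4 visit". The target of Hypothesis 1a is a "linear model of percent reduction in marijuana use on randomized treatment assignment, separately by sex"; Hypothesis 1b compares the sexes.

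Other sections aim to limit missingness. Study Adherence has staff reschedule missed visits. Subject Compensation withholds a bonus if Week 4 is missed. The data-handling text provides a Week 5 phone or email recall of Week 4 use, flagged separately in the database. Table 1 has the marijuana TLFB cover the time since the last visit.

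**The concern.** The reason given for imputing does not match what imputation does. A model that draws Week 4 from earlier observed values, with no shift or pattern-mixture term, is valid when loss is at random given those values. That is a weaker requirement than the unadjusted complete-case model makes, but it is still the assumption the sentence calls strong. It does not cover the case most feared in a cessation trial: subjects who stop attending because they are using more than their earlier visits would predict.

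The pilot exists to estimate the magnitude and direction of effects, by sex and overall, to justify a larger study. If the two models agree, a reader may take more reassurance about informative loss than the comparison can give.

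The second, conditional issue is that the named predictors do not include arm or sex, although the imputed data feed a comparison of arms within sex. If the imputation ignores arm, a smaller imputed effect could be mistaken for a sign of informative dropout when the imputation model itself produced it.

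**Working it through.** The plan states no loss rate, effect size, SD or power, so there is no figure of its own to reproduce.

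**Step 1. How much loss is possible.** Study Design says the trial will "ultimately enroll 70 subjects to ensure 40 subjects will provide a primary marijuana reduction outcome measure". The gap is (70 − 40)/70 = 30/70 = 43%, and 35 to 20 within each sex gives the same. This is an upper figure: 70 counts enrolled subjects, randomization comes later at the Baseline Visit, subjects who attend nothing after screening are replaced, and the same section has subjects "randomized to one of two treatment groups (n=20 per drug group, 50% female". I therefore show 43%, 30% and 15%.

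**Step 2. Sensitivity to loss not at random.** Let m be the fraction missing in an arm and s the percentage points by which its missing subjects fall below their imputed values. Then

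change in contrast = −(m_PRO × s_PRO − m_PBO × s_PBO).

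Assume s = 20 in PRO only. To find the shift that would remove an assumed 20-point benefit, divide 20 by m.

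| Missing | Fall in contrast | Shift that removes a 20-point gap |
|---|---|---|
| 43% | 0.429 × 20 = 8.6 | 20/0.429 = 47 |
| 30% | 0.30 × 20 = 6.0 | 20/0.30 = 67 |
| 15% | 0.15 × 20 = 3.0 | 20/0.15 = 133 |

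An equal 20-point shift in both arms changes nothing when loss is equal. It changes the contrast by 0.20 × 20 = 4.0 points when loss differs by 20 percentage points.

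**Step 3. Arm left out of a pooled imputation.** Let d be the Week 4 effect in SD units, f × d the effect at k earlier visits, ρ the common within-arm correlation, and allocation 1:1. The share of the effect kept is

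(1 − m) + m × f × sum(b), with b = S⁻¹c,

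where S is the within-arm correlation matrix plus 0.25(fd)² in every entry, and c = ρ + 0.25fd².

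Two worked ends at m = 0.429:

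- k = 1, f = 0.5, ρ = 0.3, d = 0.5: b = (0.3 + 0.03125)/(1 + 0.015625) = 0.326, so kept = 0.571 + 0.429 × 0.5 × 0.326 = 0.64.
- k = 4, f = 1, ρ = 0.9, d = 0.8: sum(b) = 4 × 1.06/4.34 = 0.977, so kept = 0.571 + 0.429 × 0.977 = 0.99.

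Ranges over assumed ρ of 0.3 to 0.9 and d of 0.5 or 0.8, with one and with four earlier visits:

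| Missing | f = 0.5, k = 1 | f = 0.5, k = 4 | f = 1, k = 1 | f = 1, k = 4 |
|---|---|---|---|---|
| 43% | 64–77% | 72–79% | 72–96% | 86–99% |
| 30% | 75–84% | 80–85% | 80–97% | 90–99% |
| 15% | 87–92% | 90–93% | 90–99% | 95–100% |

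If the earlier effect is 1.5 times the Week 4 effect, the range at 43% is 79–113% (k = 1) or 98–117% (k = 4), so inflation is possible. If earlier visits carry no effect, 57% is kept; this is unlikely, because medication starts seven days before Week 0.

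**Step 4. Simulation check.** With 70 subjects, a true effect of 0.5 SD, ρ = 0.5, an equal earlier effect and completely random loss of 43%, the mean estimate was 0.41 with arm omitted, 0.51 with arm included and 0.51 complete-case. The formula gives 0.798 × 0.5 = 0.40 for arm omitted.

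**The case against.** Several objections have force.

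- **The predictor list is not said to be complete.** Imputation is based on earlier TLFB and urine THC, but the plan does not say on these only, or that it is pooled. A model run in parallel to one fitted separately by sex may well be imputed within sex. A reader might infer that arm and sex are excluded and the imputed result is biased; the text supports only that they are not named.
- **The main analysis is not at risk from this.** It uses measured Week 4 outcomes, and imputation is additional.
- **Including arm costs precision.** In a simulation with 18 per arm-by-sex cell and 8 missing, RMSE was lower with arm omitted (0.31 male, 0.35 female) than with arm-by-sex (0.42, 0.40). The SD with arm-by-sex was 0.40 to 0.42, against 0.44 complete-case. That simulation used one summary of earlier visits with arm and sex terms, not a fuller model, and gave every dropout at least one earlier visit.
- **Imputation is not worthless against informative loss.** A reader might infer that agreement between the models says nothing. That is too strong: if Week 4 use drives loss and correlates with earlier use, imputation moves partway to the truth. In a check with a true effect of 0.5, correlation 0.7 and outcome-dependent loss in PRO only, complete-case gave 0.78 and imputation 0.65.
- **Actual loss is probably below 43%.** The Week 5 recall can recover outcomes. A subject who misses Week 4 but attends Week 5 also reports the intervening period on the TLFB.

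All five stand, and they limit the weight of the point. They do not make imputation a response to doubt about missing at random. Comparing subjects with and without Week 4 uses observed data, so it cannot detect dependence on unseen use.

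**Conclusion.** The stated rationale is wrong for the method. In the text available there is no analysis of loss not at random. Two parts of the document were not available, one of them next to the data-handling text, so a reader should not infer that the full plan certainly lacks one.

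The practical size depends on loss the plan does not state. Near 43%, a plausible one-arm shift moves the contrast by several points; at 15% the result would look robust. Nor should 43% be read as the expected dropout.

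The arm-and-sex point is secondary and conditional on a complete predictor list and pooled imputation. The imputed contrast is then usually pulled toward zero, by little at low loss or with several informative visits. Effects, correlations and shifts are all assumptions. Severity is minor to moderate.

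**What to change.** 1. **Reword the rationale.** For example: multiple imputation assumes Week 4 is missing at random given the variables in the imputation model; departures are examined in a sensitivity analysis.
2. **Specify the imputation model.** Include at least arm, sex, baseline use and the available earlier TLFB and urine THC, summarised parsimoniously. Add arm-by-sex, or impute within sex by arm, where numbers allow (about 10 observed per cell are expected). For subjects with no post-baseline visit, rely on baseline use, arm and sex.
3. **Add one pre-stated shifted-imputation analysis for Hypothesis 1a.** Lower the imputed percent reduction over a stated range (20 points could be one value) in both arms, in PRO only and in PBO only.

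Two clarifications can be made at the same time: whether the complete-case set is defined by TLFB, urine THC or both, given that the outcome is TLFB alone; and how the flagged recall outcomes enter each model.

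The cost is SAP wording and, for each shift value, three scenarios in two sexes, or six fits. The imputed estimate will have somewhat larger variance and its RMSE may rise; the change trades variance for less bias. Sensitivity results may look less favourable. Visits and data collection do not change.

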Data collected via computer programs (REDCap) will be monitored by the study coordinator by random inspection of completed forms, and any problems detected will be discussed with the PI. The SAC ([name], Director) will analyze the data using the SAS program. In addition, the SAC will provide support in developing data entry programs. Data analyses will be completed at the end of the study. For missing data: Persons who do not attend a week 4 visit, assessment of the primary outcome is not directly possible. During their week 5, study staff will attempt to contact them in order to collect by phone and/or email a self-reported recall of marijuana use as of week 4; outcomes collected in this way will be denoted separately in the study database.

Trial Safety

Potential Risks and Benefits for Participants. The potential risks for study subjects are minimal to moderate. To help protect subject privacy, we will obtain a Certificate of Confidentiality from the National Institutes of Health. The researchers can use this Certificate to legally refuse to disclose information that may identify a subject in any federal, state, or local civil, criminal, administrative, legislative, or other proceedings, for example, if there is a court subpoena. The researchers will use the Certificate to resist any demands for information that would identify a subject, except as explained below.

The Certificate cannot be used to resist a demand for information from personnel of the United States Government that is used for auditing or evaluation of Federally funded projects or for information that must be disclosed in order to meet the requirements of the federal Food and Drug Administration (FDA).

Subjects will be told that a Certificate of Confidentiality does not prevent them or a member of their family from voluntarily releasing information about themselves or their involvement in this research. If an insurer, employer, or other person obtains their written consent to receive research information, then the researchers may not use the Certificate to withhold that information.

Medical histories for all subjects will be reviewed prior to entry into the study and all subjects will be under medical supervision while in the study. Urine and breath samples will be obtained and should not present risk to the subjects. Blood samples will be obtained by trained phlebotomists. A minimal amount of blood will be collected (20cc) per collection. Blood drawing may result in slight discomfort, bruising, or there may be some soreness at the puncture site. In some cases there may be dizziness or fainting.

Progesterone is generally well tolerated. The most common adverse effect is sedation. Other less common adverse effects include menstrual irregularity (spotting or breakthrough bleeding; females only) dizziness, cramps, nausea, fatigue, headache and breast tenderness (de Lignieres, 1999; Simon, 1995, Sofuglu, 2009). Other side effects attributed to synthetic progesterone including depression, fluid retention, pruritus, jaundice, rash and thrombotic disorders, are unlikely to occur. Recently there have been reports of increased risk of stroke, coronary artery disease, venous thromboembolism and breast cancer in postmenopausal females who have been on long-term hormone replacement treatment with estradiol and progestin (medroxyprogesterone) combination (Anonymous, 2002; Grady et al., 2002; Hulley et al., 2002; Nelson et al., 2002). While some of these adverse events develop after years of treatment, venous thromboembolism is seen within the first year of treatment (Anonymous, 2002). It is possible that progestins may contribute to thromboembolism seen during estradiol and progestin treatment and thromboembolism is listed in the PDR as one of the adverse events for

medroxyprogesterone treatment (PDR, 2002). In contrast to synthetic progestins, natural progesterone is not known to cause thromboembolism (PDR, 2002). However, as a safety measure for these serious adverse events, we will exclude subjects with history of thrombophlebitis, deep vein thrombosis, pulmonary embolus, clotting or bleeding disorders, heart disease, diabetes or history of stroke. Possible adverse events from Progesterone will be assessed weekly by the research nurse ([name], NP) in consultation with the study physician ([name], MD). If the side effects cannot be tolerated the medication dosage will be decreased to 200 mg once/day for those on the active medication.

Although uncomfortable, marijuana withdrawal symptoms do not pose significant health risks. Subjects who participate in this study will be asked to quit or reduce their marijuana use on an assigned quit date. This may result in increased irritability, anxiety, tension, decreased appetite or sleeplessness.

Adverse Events: An adverse event is any unwanted experience or event occurring during the course of a clinical trial. At each visit, research assistants will collect pertinent information on any AE's and meet with the Nurse Practitioner (NP) at least once per week. The NP will decide if the AE was related to the study medication and give recommendations for follow-up. In cases where the NP is unavailable or if the AE needs immediate attention, it will be escalated to the PI immediately for acknowledgment and recommendations.

The study investigators will follow all AEs to the point of a satisfactory resolution. A study subject may be withdrawn from the study if the PI determines it is the best decision for protection of the safety of the subject. All AEs will be assessed to determine if they meet criteria for an SAE. AEs will be quantified separately by sex and treatment groups and compared across treatment groups with Fisher's exact test (for binary events) or with chi-square test (for counts of events or event rates). The event will be documented as to whether there is 1) no relationship between the study drug and the adverse event, 2) the adverse event is unlikely related to administration of the study drug, 3) the adverse event is possibly related to study drug administration, or 4) the adverse event is probably related to the administration of the study drug.

Serious Adverse Events (SAE): A serious adverse event is defined as an outcome that is 1) fatal or life-threatening, 2) significantly or permanently disabling or incapacitating, 3) requires or prolongs inpatient hospitalization, or 4) results in a congenital anomaly. SAE's, whether or not related to study medication, will be reported to the IRB and NIDA. All drug related adverse events of a non-serious nature are reported to the University of Minnesota's IRB on an annual basis. Serious adverse events will be reported by telephone to the IRB, and to NIDA and the FDA within the three days of our receipt of information regarding the event and written reports will be submitted within ten days. If a subject either withdraws from the study or the investigator decides to discontinue a subject due to SAE, the subject will have appropriate follow-up medical monitoring. Monitoring will continue until the problem requiring hospitalization was resolved or stabilized with no further change expected, is clearly unrelated to study medication, or results in death. Outcome of SAEs will be periodically reported to NIDA. A summary of the SAEs that occurred during the previous year will be included in the annual progress report to NIDA. Finally, the PI will ensure that serious adverse events are reported to NIDA via the serious adverse event tracking and reporting system at <https://saetr.snia.nih.gov/>.

The Principal Investigator will then take appropriate action (including study modification) as agreed upon by these monitoring groups including the DSMB when needed. The Principal Investigator will determine whether the seriousness of the event warrants removal of the participant from the study. Appropriate diagnostic and therapeutic interventions will be initiated and the participant will be medically followed and kept under observation as long as medically indicated. After the review of the data, the DSMB report will make recommendations about whether the trial should continue with or without modifications, or be terminated. Any potential conflict of interest in the Data and Safety Monitoring Board will be disclosed.

Protection against Risk. Subjects will be told the potential risks involved in this study. Although risks to subjects in the proposed study are minimal, the following actions will be taken to minimize these risks. We will exclude subjects with health conditions that may be exacerbated by their participation. Subjects will be monitored regularly by medical personnel employed by the study. [name] (PI) will be available for emergency phone calls 24 hours/day and for office visits in case of problems. Blood will be collected by trained phlebotomists to reduce the risks involved with blood draws.

During Progesterone administration, the first dose of the study medication will be taken at 8 PM to minimize possible sedation from initiation of progesterone treatment. Subjects will be warned about using caution when driving a motor vehicle or operating machinery. Subjects will also be warned about the side effects associated with Progesterone. Further, although unlikely, the study physician ([name], PI) will be alert to the earliest

manifestations of thrombotic disorders including thrombophlebitis, cerebrovascular disorders, pulmonary embolism, and retinal thrombosis (PDR, 2002). If any of these occur or are suspected, the study medication will be discontinued immediately and medical treatment will be sought.

Potential Benefits of the Proposed Research to the Subjects and Others

Whereas no assurance can be made to an individual subject that he/she will personally benefit from such research, the experience should be beneficial. Subjects will have the opportunity to learn about their marijuana use behavior and receive behavioral counseling. Society may benefit from a better understanding of the role of sex hormones on marijuana use and impulsivity. A better understanding of this relationship will help improve treatment strategies for marijuana use. The risks in relation to the potential benefits are minimal to the individual research subject and virtually nonexistent to society in general.

Trial Efficacy

No interim analyses of efficacy are planned for the proposed study.

References

Adamson, S. J., & Sellman, J. D. (2003). A prototype screening instrument for cannabis use disorder: the Cannabis Use Disorders Identification Test (CUDIT) in an alcohol-dependent clinical sample. *Drug and Alcohol Review*, 22(3), 309–315. [PMID: 15385225]

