Study Adherence: To encourage compliance the following will occur: (1) at the Baseline Visit, subjects will be given a schedule of all remaining appointments; (2) at each visit the subjects will be given an appointment reminder card for the next visit; (3) reminder calls, texts and/or emails (per subject's preference) will be placed or sent the day before each visit; (4) subjects will be routinely reminded that regardless of their marijuana use that their data are valuable and important; and (5) regardless of marijuana use, subjects will be compensated at each visit (described below). If a subject misses a visit, study staff will try to reach him/her by phone that day to reschedule for one to three days later. If that does not work, staff will contact the subject's designated 'contact person' (i.e., someone who does not live with the subject but knows how to get in touch). If a subject does not attend any visits after the screening visits, he/she will be labeled as a "drop" and replaced. If the subject discontinues from the study after randomization but before the final follow-up visit, he/she will be labeled an "*incomplete*" but not replaced. If a subject does not quit on their assigned quit date or relapses later, she/he will be encouraged to stay in the study and make another quit attempt; such that we will follow them for the length of the study regardless of marijuana use. Subjects who complete the weekly follow-up period after quit date, regardless of marijuana use, will be labeled a "*completer*" for the primary outcome and not replaced.

[figure not shown]
THC Urine Dipstick Test: The THC Urine Dipstick Test

is a one-step immunoassay that qualitatively detects delta-9-tetrahydrocannabinol in urine. The results obtained are of a preliminary nature and is for screening purposes only. THC, psychoactive component of marijuana, is a central system stimulant relaxant. THC in marijuana is strongly absorbed by fatty tissues in various organs and a metabolite form of THC, delta-9-tetrahydrocannabinol, is present in urine 48-72 hours after a smoking-session. This is what denotes a marijuana user.

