Therefore, subjects will receive approximately \$340 (\$25 Screening Visits x 2 visits + \$20 follow-up visits x 7 visits + \$80 in bonus payments + an average of \$70 in BART payments).

Study Medication

Subjects will be stratified by sex and then randomly assigned to PRO or PBO, as described above. All medication (active and placebo) will be prepared by the University of Minnesota Clinical Trials Research Pharmacy, which is a specialized facility that prepares medication for clinical trials including our ongoing research. The research pharmacist ([name] Pharm D) will provide medications. There will be oversight and monitoring with regular audits by local regulatory boards including the IRB and DSMB. This study requires double-blind procedures, therefore progesterone will be over encapsulated and be identical to the placebo capsules. Medications will be discontinued at the Week 4 clinic visit. Adverse events will be assessed at each clinic visit.

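### New adverse events are not solicited from subjects who stop attending, although the plan already contacts them for other purposes

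*Combined protocol and SAP*

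**What the plan says.** Solicited safety collection is described as a visit activity. Study Medication says "Adverse events will be assessed at each clinic visit". The Adverse Events paragraph under Trial Safety says "At each visit, research assistants will collect pertinent information on any AE's". The account of Weeks 0-5 also places AE assessment within the visit, where a new one-week supply is handed out. The C-SSRS entry schedules that scale at clinic visits and gives as its reason that suicidal ideation is a serious event on the product label. Table 1 shows both instruments only in visit columns, with the AE item covering the time since the last visit.

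Two contacts with non-attenders are described:

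- Study Adherence: after a missed visit, "study staff will try to reach him/her by phone that day to reschedule for one to three days later", and then staff try a designated contact person.
- The missing-data paragraph just before Trial Safety: in Week 5, staff try to reach those who missed Week 4 and "collect by phone and/or email a self-reported recall of marijuana use as of week 4". These outcomes are marked separately in the database.

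The Adverse Events paragraph plans by-arm comparisons with Fisher's exact or chi-square tests. It states no denominator, no exposure time and no rule for incomplete AE follow-up. The missing-data plan covers only marijuana outcomes.

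On expected loss, Study Design says the trial will "ultimately enroll 70 subjects to ensure 40 subjects will provide a primary marijuana reduction outcome measure at four weeks post quit date".

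**The concern.** The plan recovers efficacy data remotely from people it has lost, but states no such step for safety data. Someone who leaves because the capsules made them sleepy or unwell would be asked about marijuana, not about why they stopped. The protocol names sedation as the most common effect of progesterone, so dropout linked to an AE on the active arm is plausible. If it happens and the event is not recorded, the progesterone AE rate is too low and the arm difference shrinks. This is a pilot meant to justify a larger trial, so tolerability is one of its main products. Serious-event reporting also runs from receipt of the information, so it depends on someone asking or telling.

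**Working it through.** **1. Does any existing provision ask a lost subject about new events?**

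| Provision | Needs |
|---|---|
| AE and C-SSRS at visits (Study Medication, Adverse Events, Table 1) | attendance |
| AE question since the last visit (Table 1) | a later visit, Week 5 included |
| Weekly assessment by the research nurse (Trial Safety) | mode not stated; the weekly contact described elsewhere is the visit |
| Follow-up to resolution (Adverse Events) | an AE already known |
| Monitoring after withdrawal for a serious event (Serious Adverse Events) | a serious event already known |
| 24-hour phone access (Protection against Risk) | the subject calls |
| Missed-visit call (Study Adherence) | stated purpose: rescheduling |
| Week 5 phone/email contact (missing-data paragraph) | stated content: marijuana use |

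None of these, as written, asks a subject who does not return about new events.

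**2. How many could be affected?** Inputs from Study Design: 70 enrolled, 40 with a Week 4 outcome. The plan states no dropout rate, so there is no figure of its own to reproduce.

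- Ceiling: (70 − 40)/70 = 30/70 = 42.9%.
- Under Study Adherence, subjects who attend nothing after screening are drops. They miss Baseline, so they are not randomized or given medication. If k of the 30 are such drops and count among the 70, the share of those randomized is (30 − k)/(70 − k):
  - k = 5: 25/65 = 38%
  - k = 10: 20/60 = 33%
  - k = 15: 15/55 = 27%
  - k = 20: 10/50 = 20%
- Subjects who miss Week 4 but attend Week 5 lower the share further.

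**3. How many AE assessments would be missed?** There are six visits after the first dose (Weeks 0 to 5). Assume that lost subjects never return and that their first missed visit falls evenly over Weeks 0 to 4. The mean number missed is (6 + 5 + 4 + 3 + 2)/5 = 4. With 70 × 6 = 420 planned assessments:

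- 10 lost: 40/420 = 9.5%
- 20 lost: 80/420 = 19.0%
- 30 lost: 120/420 = 28.6%

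Each such subject left the last attended visit with a one-week supply, so up to 7 days at two doses a day (14 doses) of exposure may go unassessed.

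**4. What could it do to the comparison?** The documents give no AE rates, so this is illustration only. Assume true risks of 50% (progesterone) and 20% (placebo), 35 per arm, and Fisher's exact test at two-sided 5%. With full recording the difference is 30 points and power is 69%. Suppose an extra share of the progesterone arm leaves through intolerance:

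| Extra share leaving | None of their AEs recorded: difference, power | Half recorded: difference, power |
|---|---|---|
| 5% | 25 points, 53% | 27.5 points, 61% |
| 10% | 20 points, 36% | 25 points, 53% |
| 20% | 10 points, 10% | 20 points, 36% |

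If all are recorded, there is no loss.

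**The case against.** The strongest reply is that safety oversight does not end with the last visit. Known AEs are pursued, serious events are monitored after withdrawal, a phone line is open at all hours, staff try a contact person, and the AE question at any later visit reaches back over the gap. All of this stands. It limits the gap to new, unreported events in people who never return.

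A reader might infer that safety data stop for 43% of subjects. The documents do not support that. The 43% is the gap between enrolment and the target for Week 4 outcomes. It may include people who never took a capsule and people seen again at Week 5. Study Design also gives 20 per drug group; read literally, only 40 are randomized and the loss could all come before dosing. That reading fits poorly with Study Adherence, which does not replace subjects who leave after randomization, and with the Week 5 recovery contact. Still, it confirms that 43% is a ceiling.

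A reader might also infer that the AE comparison is biased. Nothing in the documents shows that non-attenders leave because of AEs; Study Adherence equally foresees failed quit attempts and relapse. Nor is under-recording the only weakness. With assumed risks of 45% and 10% and full recording, Fisher's test has 89% power at 35 per arm, 62% at 20 and 22% at 10 (one sex, 20 per group). Small size alone limits what the comparison can show.

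Finally, the Week 5 sentence is a rule for the primary outcome, not a full call script, and staff may ask about AEs in practice. Some text shortly before it was not available for this review, so a safety-contact provision there cannot be excluded.

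**Conclusion.** The point holds as a specific gap, with moderate confidence. As written, the plan does not solicit new AEs from subjects who stop attending, although it contacts them for other reasons. At most 30 of 70 enrolled are affected (43%). The share is about 20% to 38% of those randomized if 5 to 20 of the 30 never received medication, and lower still with returns at Week 5. The by-arm comparison may understate harm on progesterone. That requires AE-related dropout on the active arm with the event unrecorded, and the documents do not allow its size to be estimated. The power figures above rest on assumed risks and should not be read as predictions. This is a cheap improvement to safety ascertainment, not a flaw that invalidates the trial.

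**What to change.** In Study Adherence and in the missing-data paragraph before Trial Safety, state that each missed-visit call and the Week 5 phone/email contact also asks for:

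- the standard AE question since the last visit;
- any hospitalisation or emergency care;
- the reason for stopping;
- the date of the last dose.

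Record the answers on the AE form, flagged as remote, as the plan already does for remote marijuana recall. Send any serious event through the existing Serious Adverse Events reporting path. Report AEs by arm with and without the remote reports. Administering the C-SSRS by phone is optional, if trained staff make the call.

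The cost is protocol wording, a short script and IRB approval of the change; no new visit is needed. The downside is that remote reports are less detailed, which is why they are flagged and why both tabulations are shown.
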